4.2.1 Eligibility Criteria

Prior to inviting participants into the pilot study, we will screen the CHARIOT Register volunteers for exclusion criteria based on available information recorded against their register profile. Screening eligibility will also be self-assessed upon study invitation. To facilitate ease of assessment, the inclusion/exclusion criteria are brief and specific. The study welcome message and Participant Information Sheet will detail the eligibility criteria for potential participants to review and make a self-assessment as to whether they meet the eligibility criteria. Prior to completing the Informed Consent Form, participants will be asked to confirm their eligibility. If they select 'no' next to any inclusion or 'yes' next to any exclusion criteria, they will be notified of their non-eligibility at that time. We understand that volunteers may be disappointed if they do not meet the eligibility criteria. If a volunteer does not meet screening eligibility, they will be informed of the decision, thanked for their time and

be provided with a description of the exclusion criteria and why these criteria are considered exclusionary for the purposes of this study. The excluded individual will also be provided with links to resources on topics relating to physical activity and NHS recommendations for maintaining a healthy lifestyle (which form the resources provided to the control group).

4.2.2 Inclusion Criteria

- Aged 60+ years
- No dementia diagnosis (self-reported)
- Has access to the internet and a suitable device
- English competency and no significant visual or auditory disability (able to read, hear (including with a hearing aid) and write)
- Able to ambulate safely with or without a walking aid.
- Able to participate in gentle exercise without any contraindication from a healthcare professional (note that no permissions are needed; if they have not been told otherwise, it is assumed there is no contraindication to daily physical activity)

4.2.3 Exclusion Criteria

- Dementia diagnosis or prescription of dementia specific medicines, as per NICE guidelines (16)
- Severe loss of vision, hearing, or communicative ability; conditions preventing cooperation
- Limited or no access to technology or insufficient confidence in doing so
- Participation in another intervention study
- Chest pain on exercise
- Dizziness on exercise

4.4 Withdrawal Criteria

All participants have the right to withdraw from the MOU pilot study at any time, without providing a reason. Participants may withdraw by contacting the study team directly or they can select to withdraw electronically by following a link provided to them within each study email. At the time of withdrawal, participants may be asked whether they would like to share any comments of their experience on the study and their reason for withdrawing. The

participant is not obliged to provide this information, but if they do provide a reason, this information will be recorded. All information already collected as part of the study will be retained for analysis, but no further data will be collected from them.

Only those participants who discontinue participation in all study activities will be considered as withdrawn. All discontinuations, including transient, will be automatically documented during the study. Participants who withdraw voluntarily will also have the possibility to return to the study, or to return to the study activities, provided they are still ongoing.

At time of any future protocol amendment notification, if a participant fails to re-consent after receiving a reminder email to do so, they will be considered withdrawn unless they contact the study team to notify of their interest in re-participation.

5. ADVERSE EVENTS

All the physical activities suggested in the digital tool are of low-impact, and designated as safe for participants in this age group by the research team including: sport and exercise medicine professionals, physiotherapists and exercise rehabilitation instructors. Moreover, participants embarking on either the control or intervention arms will be reminded that they should not participate in anything with which they feel uncomfortable or incapable, and that participation is at their own risk.

Collecting and reporting study events will help to protect the safety of clinical study participants and fulfill regulatory responsibilities. This section describes the requirements and procedures for study event reporting, even though no specific investigational medicinal products are being studied. Participants will be provided with a link to a form to complete in the event of any adverse event, so that these may be logged and followed-up.

5.1 Definitions

Adverse Event (AE): any untoward occurrence in a participant. These might include injuries from participation in the activities suggested by the digital rehabilitation tool.

Serious Adverse Event (SAE): any untoward and unexpected occurrence or effect that:

- Results in death
- Is life-threatening – refers to an event in which the participant was at risk of death at the time of the event; it does not refer to an event which hypothetically might have caused death if it were more severe
- Requires hospitalisation
- Results in persistent or significant disability or incapacity

Medical judgement will be exercised in deciding whether an AE is serious and/or severe in all situations. Important AEs that are not immediately life-threatening or do not result in death or hospitalisation but may jeopardise the participant or may require intervention to prevent one of the other outcomes listed in the definition above, will also be considered serious.

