5.2 Reporting Procedures

Any events that are reported by the participant to have taken place from the time of signing the informed consent to study termination will be reported as adverse or serious adverse event, depending on which criteria are being met. Depending on the nature of the event the reporting procedures below will be followed. All adverse events (AEs) should be reported. Any questions concerning adverse event reporting should be directed to the Principal Investigator in the first instance. Adverse events will be recorded by participant study ID

numbers. No identifiable information in relation to any adverse events reported will be disclosed outside of Imperial College London.

Non-serious Adverse Events (AEs)

All such events, whether expected or not, should be recorded. This will include concerns raised by participants from completing the questionnaires, including anxiety, or events that occur during the course of the study that the participant feels may affect their participation.

Serious Adverse Events (SAEs)

A Serious Adverse Event (SAE) form should be completed and emailed to the Principal Investigator within 24 hours.

Contact Details for Reporting SAEs:

Phone: [[name]]

Email: [contact]

FAO: [name]

Note that hospitalisations for elective treatment of a pre-existing condition do not need reporting as SAEs

All SAEs should be reported to the Ethics and Research Governance Coordinator where in the opinion of the Principal Investigator, the event was:

- 'related', i.e. resulted from the administration of any of the research procedures; and
- 'unexpected', i.e. an event that is not listed in the protocol as an expected occurrence

Local investigators should report any SAEs as required by their Local Research Ethics Committee,

Sponsor and/or Research & Development Office.

SAE Forms must be sent to the JRCO administrator in the Joint Research Compliance Office – Email:

[contact]

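### Protocol Section 5.1 makes unexpectedness part of the SAE definition, which contradicts the separate expectedness test in Section 5.2 and may lead to serious events being misclassified

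*Protocol*

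**What the plan says.** Protocol Section 5.1 defines the two event classes differently. For adverse events it has "Adverse Event (AE): any untoward occurrence in a participant", with no condition on expectedness, and it adds the example "These might include injuries from participation in the activities suggested by the digital rehabilitation tool". For serious events it has "Serious Adverse Event (SAE): any untoward and unexpected occurrence or effect that", followed by four outcomes: death, threat to life, hospitalisation, and lasting or significant disability. It goes on: "Medical judgement will be exercised in deciding whether an AE is serious and/or severe in all situations". The next sentence extends seriousness to important events that fall short of immediate threat to life, death or hospitalisation.

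Section 5.2 says that participant-reported events "will be reported as adverse or serious adverse event, depending on which criteria are being met", and that "All adverse events (AEs) should be reported". Under its heading for non-serious events it says "All such events, whether expected or not, should be recorded". Under its heading for serious events it requires an SAE form to reach the Principal Investigator within 24 hours. It then sends onward those SAEs that are both related and unexpected, where unexpected means "an event that is not listed in the protocol as an expected occurrence".

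**The concern.** Seriousness describes the outcome of an event. Expectedness describes whether the event was anticipated. Section 5.1 merges the two and Section 5.2 treats them as separate attributes, so the protocol gives an assessor two incompatible rules.

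The class of event exposed to this conflict matters. The one kind of event that Section 5.1 names in advance is injury from the tool's own exercises, in participants aged 60 or over. If such an injury leads to hospital admission and is judged foreseeable, a literal reader of Section 5.1 would not call it an SAE. Safety is objective (ii) in Section 2 and part of the hypothesis in Section 1.2, so the label and the speed of notification should not depend on which sentence the assessor reads first.

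**Working it through.** No arithmetic applies. The protocol gives no AE or SAE rate and no list of expected events, so the check is a comparison of the texts.

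**1. Does the Section 5.2 filter do anything under the Section 5.1 definition?**
- Section 5.1: SAE = untoward + unexpected + (a listed outcome).
- Section 5.2: onward report = SAE + related + unexpected.
- Substituting the first into the second, the second *unexpected* is already satisfied by every SAE and removes nothing. The filter has content only if SAE = untoward + (a listed outcome). The two sections therefore assume different definitions.
- Section 5.2 also exempts admissions for elective treatment of a pre-existing condition from SAE reporting. Such admissions are planned, so the exemption would be largely unnecessary if expected events were already outside the definition. This again suggests that Section 5.2 was written for a definition without the expectedness condition.

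**2. What counts as expected?**
The only definition is the one in Section 5.2, by reference to a listing in the protocol. No part of the protocol is headed or described as a list of expected occurrences. The nearest text is the example of tool-related injuries in Section 5.1. Two readings follow:

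| Reading | Consequence for a hospitalised injury from the tool's exercises |
|---|---|
| A. Nothing is listed, so every event is unexpected | It is an SAE; the form and 24-hour notice apply; no SAE is lost |
| B. The Section 5.1 example counts as a listing | It is expected, so outside the SAE definition; no SAE form or 24-hour notice is required |

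Under reading B the affected injuries can arise only in the intervention arm, because only that arm receives the tool.

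**3. Does other text repair reading B?**
- *Medical-judgement clause.* Its first sentence leaves seriousness to judgement but does not tell the assessor to disregard expectedness. Its explicit extension covers important events short of death, immediate threat to life or hospitalisation, so it does not expressly bring a hospitalised, expected injury back in.
- *Recording whether expected or not.* This phrase stands only under the non-serious heading. A serious but expected event fits neither heading of Section 5.2 cleanly.
- *Reporting of all AEs.* This does apply. Under reading B the event remains an AE and is to be reported as one.

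**4. What reaches the safety data in either case?**
Section 2 states the safety objective as a self-reported profile, not as an SAE count. Section 5 gives participants a form for any adverse event, and Section 4.1.4 adds safety items to the follow-up questionnaires sent to every participant. Under reading B the event keeps its place in the data but carries the wrong label and misses the expedited route.

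**The case against.** The strongest reply is that the word removes nothing. By the protocol's own definition an event is unexpected unless listed, and nothing is listed, so every event with a serious outcome qualifies. The example in Section 5.1 illustrates what an AE is. It is not presented as a list and does not mention hospitalisation or death. Section 5 describes the activities as low-impact and judged safe, which would make a serious injury from them unexpected. The medical-judgement clause also starts from any AE and applies in all situations.

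Much of this stands. Reading A is tenable and under it the loss is zero. It does not remove the contradiction, however. The definition of *unexpected* sits in Section 5.2, attached to the onward-reporting test, and Section 5.1 does not refer to it. An assessor applying Section 5.1 by itself may give the word its ordinary sense, and the protocol offers nothing to settle the matter. The judgement clause allows the right classification but does not secure it.

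A reader might go further and infer that the safety objective as a whole is undercounted, mainly in the intervention arm, and that a comparison of SAEs between arms is biased towards the tool. The protocol does not support that. A misclassified event is still reported as an AE, the objective is not limited to SAEs, and no between-arm comparison of SAEs is specified. The arm imbalance depends on reading B.

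**Conclusion.** The contradiction between Sections 5.1 and 5.2 is plain on the page and should be corrected. Its supported consequence is limited: a serious, tool-related injury that is judged foreseeable could be filed as a non-serious AE, miss the SAE form and the 24-hour notification, and leave the SAE count low. Because only the intervention arm uses the tool, any such understatement would fall more on that arm.

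This rests on one assumption, that an assessor treats the Section 5.1 example as making those injuries expected. If no event counts as listed, no SAE is lost. The size lies between zero and all serious tool-related injuries outside the reach of the judgement clause. It cannot be narrowed, because any percentage would rest on event rates that the protocol does not give.

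**What to change.** Reconcile the two sections:

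- In Section 5.1, delete the words *and unexpected* from the SAE definition, so that seriousness depends on the listed outcomes and the medical-judgement clause.
- In Section 5.2, keep relatedness and expectedness as the test for onward reporting only, and state there which events are regarded as expected, or that none are.
- State that SAEs will be reported by arm irrespective of expectedness.

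The cost is a short protocol amendment and possibly a few more SAE forms. The design, the sample size and data collection from participants do not change.

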5.2 Reporting Procedures

Any events that are reported by the participant to have taken place from the time of signing the informed consent to study termination will be reported as adverse or serious adverse event, depending on which criteria are being met. Depending on the nature of the event the reporting procedures below will be followed. All adverse events (AEs) should be reported. Any questions concerning adverse event reporting should be directed to the Principal Investigator in the first instance. Adverse events will be recorded by participant study ID

numbers. No identifiable information in relation to any adverse events reported will be disclosed outside of Imperial College London.

Non-serious Adverse Events (AEs)

All such events, whether expected or not, should be recorded. This will include concerns raised by participants from completing the questionnaires, including anxiety, or events that occur during the course of the study that the participant feels may affect their participation.

Serious Adverse Events (SAEs)

A Serious Adverse Event (SAE) form should be completed and emailed to the Principal Investigator within 24 hours.

Contact Details for Reporting SAEs:

Phone: [[name]]

Email: [contact]

FAO: [name]

Note that hospitalisations for elective treatment of a pre-existing condition do not need reporting as SAEs

All SAEs should be reported to the Ethics and Research Governance Coordinator where in the opinion of the Principal Investigator, the event was:

- 'related', i.e. resulted from the administration of any of the research procedures; and
- 'unexpected', i.e. an event that is not listed in the protocol as an expected occurrence

Local investigators should report any SAEs as required by their Local Research Ethics Committee,

Sponsor and/or Research & Development Office.

SAE Forms must be sent to the JRCO administrator in the Joint Research Compliance Office – Email:

[contact]

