2. STUDY OBJECTIVES

The primary study objective is to pilot a randomised controlled trial of a digital rehabilitation tool and to assess the feasibility for a larger randomised controlled trial. Objectives will cover:

- (i) Impact on effect sizes (pilot RCT): for both the proposed primary outcome on self-reported physical activity (MET/minutes per week) and secondary outcomes of physical literacy and mood
- (ii) Safety: self-reported safety profile
- (iii) Feasibility: recruitment rate, attrition rate, follow-up rate for questionnaires; adherence and usage of the digital tool
- (iv) Usability: perceptions of usability and impact; perceived barriers to inclusion

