All participants will be invited to join the study through an email of a flyer on an invitation email distributed through the secure Imperial Qualtrics platform to eligible people on the CHARIOT register. The distribution list will be managed such that automated follow-ups will be sent at 3 and 6 months, provided the participant has not opted out of the study. . If no response is received, an automated follow up email will be sent. A study-specific email address will be provided to potential participants ([contact]) should they wish to ask any further questions, and it will be made clear to participants that they can opt out or withdraw from the study by clicking the dedicated link. The invitation flyer on the email / letter will include a unique link connected to a participants study (CHARIOT) ID number, which will direct them to the Qualtrics Platform, and will also contain an ~~and~~ embedded dedicated study ID also to pseudoanonymise respondents. Distribution will be managed via Qualtrics by the AGE team. On clicking the link/scanning the QR code, participants will receive a welcome message and will be prompted to read the Participant Information Sheet. The welcome message and Participant Information Sheet will outline the pilot's eligibility criteria for participants to do a self-screening assessment and will request participants to only progress onto completing the Informed Consent Form (ICF) if they fulfil all eligibility requirements. Prior to the ICF, participants will be asked to confirm that they meet the eligibility requirements.

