4.1.4 Follow-up and study flow

Follow-up questionnaires (the same as baseline questionnaires but without demographic information, and with added components on safety and feasibility) will be sent to each participant at 3 months from completion of the baseline questionnaire, and again at 6 months using the Qualtrics platform Funding will be sought to send further follow-up questionnaires at 1 year and again at 2 years, and these follow-up windows will be included in consent process at the start of the study.

[figure not shown]

Figure 3: Study flow

Participants will be recruited and randomised following informed consent. Randomisation will be to intervention (Movement Foundations digital tool) or control groups (educational resources only) at a 1:1 rate. All participants will receive baseline questionnaires at time=0, mid-point questionnaires at time=3 months, and end-point questionnaires at time=6 months.

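### Serious adverse events include death and lasting incapacity, but every reporting route described depends on the participant and nobody else is invited to report

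*Protocol*

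**What the plan says.** Protocol section 5.1 lists the criteria for a serious adverse event. The first is "Results in death", and a later one is "Results in persistent or significant disability or incapacity".

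Section 5.2 says which events enter the reporting process: "Any events that are reported by the participant to have taken place" between consent and the end of the study. It adds a general instruction that all adverse events be reported, and it requires a serious event form to reach the Principal Investigator within 24 hours. It does not say how the person completing that form would learn of the event.

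The routes by which an event can become known are described in two other places:

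- Section 5: "Participants will be provided with a link to a form to complete in the event of any adverse event".
- Section 4.1.4: the 3- and 6-month questionnaires repeat the baseline set "with added components on safety and feasibility".

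Section 2 names the objective accordingly: "Safety: self-reported safety profile". Section 1.2 asks about the tool's safety profile and hypothesises that its use will be safe, with no restriction to people who respond.

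On silence from a participant, section 4.1.1 says: "If no response is received, an automated follow up email will be sent". Section 2 also makes "recruitment rate, attrition rate, follow-up rate for questionnaires" feasibility outcomes.

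**The concern.** The intake rule and the definition do not fit together. A person cannot report their own death, and a person left permanently unable to use the form or the questionnaire cannot report that either. These are the gravest events the protocol defines, and they are the ones for which it describes no way in.

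Participants are aged 60 or over, may use a walking aid, and exercise remotely through a web-based tool. No in-person visit is described at which staff would learn of a serious event. If one happens and nobody outside the study has been asked to report it, what the team sees is an unanswered questionnaire.

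What is at stake is how far a reassuring result can be read. A count of no deaths and few serious events would be weak evidence for the safety hypothesis, because the same count could arise when such events had occurred. The pilot is meant to inform a larger trial, which could inherit both the conclusion and the reporting procedure.

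**Working it through.** The protocol states no death rate, serious event rate or safety-based sample size, so there is no figure to reproduce. The check is to follow an event from occurrence to record.

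**Step 1. Who can trigger a record?**

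| Place in the protocol | Route or duty | Needs the participant to act? |
|---|---|---|
| 5 | Adverse event form link | Yes, the link is given to participants |
| 4.1.4 | Safety items at 3 and 6 months | Yes, participants complete the questionnaire |
| 5.2, opening rule | Classification as adverse or serious | Yes, as worded |
| 5.2, general instruction and 24-hour form | Duty to report | Source not stated; applies once someone knows |
| 4.4 | Reason for withdrawal | Yes, recorded only if the participant gives one |
| 4.1.1 | Response to silence | An automated email; no other contact described |

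No passage describes a relative, carer or clinician as a reporter, and none describes a check of vital status. The sentence in 4.1.1 about non-response stands among text on both the invitation and the follow-up mailings. Whichever it refers to, nothing beyond an email is described.

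**Step 2. Apply this to the definitions in 5.1.**

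- Death: no described route leads to a record.
- Incapacity or a life-threatening event after which the participant never responds again: the same.
- Hospitalisation, injury or disability in someone who can still respond: the form link and the later questionnaires both allow a report after the event. The gap does not apply here.

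**Step 3. What trace remains?** In the first two cases the trace is non-response. Someone who lost interest leaves the same trace, so the data cannot tell the two apart.

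**Step 4. Illustration of scale.** The only document inputs are the maximum of 1000 participants (section 4.1.1) and the 6-month questionnaire (section 4.1.4). Annual mortality *m* is an assumption.

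- 6-month risk: p = 1 − (1 − m)^0.5
- Expected deaths: 1000 × p
- Chance of at least one: 1 − (1 − p)^1000

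| Assumed annual mortality | 6-month risk p | Expected deaths | Chance of at least one |
|---|---|---|---|
| 0.25% | 0.125% | 1.25 | 71% |
| 0.5% | 0.25% | 2.50 | 92% |
| 1% | 0.50% | 5.01 | 99% |
| 2% | 1.01% | 10.05 | above 99.9% |

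The expected number falls in proportion if fewer than 1000 enrol. If non-response were 20% to 30% (also assumed), these few deaths would sit unmarked among 1000 × 0.20 = 200 to 1000 × 0.30 = 300 non-responders.

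**The case against.** The strongest reply is that section 5.2 is a rule of inclusion. It says that what participants report will be classified; it does not say that nothing else will be. Section 5.1 defines an adverse event by what happened to the participant, whoever reports it. Section 5.2 also tells staff to report all adverse events, gives contact details for serious ones, and mentions local investigators. A reader might infer from the opening rule that no death could ever be recorded. The text does not support that: a death the team heard of could be logged. But these duties start once someone is aware of the event, and nothing described brings that awareness about.

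A reader might also infer that the protocol counts deaths as attrition. It has no such rule. Section 4.4 is silent on death, and the likeness to non-response follows from the procedures only when nobody tells the team.

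Third, self-report is declared openly in section 2, and this is an unfunded online pilot of low-impact exercise. Complete ascertainment of deaths is not promised and would be out of proportion. That is fair, and it limits what can be asked for. It does not reconcile the intake rule with the definition, or with the unrestricted safety hypothesis in section 1.2.

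Fourth, most deaths in this age group would probably be background events in both arms, and nothing here shows that missing them would bias the comparison between arms. That stands, and no such bias is claimed.

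**Conclusion.** The point holds in a limited form. Sections 5.1 and 5.2 need to be reconciled: the protocol defines death and persistent incapacity as serious adverse events, but describes no procedure by which a death, or an event that ends all further response, would come to the team's notice other than by chance. The finding rests on the wording of the protocol and on the absence of any described proxy or vital-status route.

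Its size cannot be taken from the document. Under the assumed mortality range, at least one death during 6 months at full recruitment is more likely than not, but the argument does not depend on the rate.

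A reader might go further and conclude that non-responders will be treated as free of events, or that the safety denominator is wrong. The protocol sets no safety denominator. That is commonly left to a statistical analysis plan, which is not available here, so no criticism is made on that score. Events in participants who can still answer are not affected.

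**What to change.** Make three small changes.

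1. In section 5.2, widen the intake rule so that it covers events reported by the participant, or on their behalf by a relative, carer or clinician, or otherwise learned of by the study team. The existing form link can serve all of them.
2. Add one line to the automated emails already planned, inviting such reports.
3. Limit the safety conclusion to self- or proxy-reported events, and state that the vital status of non-responders is not ascertained.

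The cost is one amended sentence, one line of email text and one qualifying statement. No register linkage, GP check or extra staff is needed.

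The price is a narrower safety claim. The change does not close the gap completely: proxy reports depend on someone seeing the invitation and acting on it, so ascertainment of deaths will stay incomplete.

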6. ASSESSMENT AND FOLLOW UP

6.1.1 Questionnaires

Questionnaires provided as part of the baseline, mid-point and end-point assessments for all participants will consist of a combination of previously validated tools and stand-alone questions. Below provides a summary of each component within the questionnaire. The questionnaire has been designed in alignment with that used in other studies within the CHARIOT register, such as the CHARIOT COVID-19 Rapid Response study (CCRR) (April 2020) and includes:

Demographics

Sociodemographic variables include age, sex, ethnicity, education, occupational status and history, annual gross household income, household composition, marital status and postcode.

Medical history and biometrics

Existing co-morbidities and medications will be collected via self-reporting. Baseline biometrics including weight, height and most recent record of blood pressure measurement (where available) will be included. Participants will be asked to report on their current mobility status and frequency of access to primary care.

Mood

Anxiety and Depression: The Hospital Anxiety and Depression Scale (HADS) tool will be utilised for this study.²³ HADS includes 14 questions on feelings related to anxiety and depression rated on a 4-level Likert scale from “most of the time” to “not at all”. The HADS tool has face validity, with questions that are easy to relate to and appropriate to the current social isolation situation. The tool is also widely used and easy to score.

Sleep Quality

Physical activity has impacts on sleep quality²⁴ and reduced quality of sleep is a risk factor for the development of cognitive deficits and dementia.³

The Pittsburgh Sleep Quality Index -PSQI ²⁵ measures sleep quality with good validity and test-retest reliability.²⁶

Physical Activity

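### The SAE exemption for elective admissions is not limited to conditions that have not worsened since consent

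*Protocol*

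**What the plan says.** Section 5.1 of the protocol defines an SAE as an untoward and unexpected occurrence that meets one of four criteria. One is "Requires hospitalisation"; another is "Results in persistent or significant disability or incapacity". It adds: "Medical judgement will be exercised in deciding whether an AE is serious and/or severe in all situations". A further sentence treats as serious those important events that stop short of death or hospitalisation but "may jeopardise the participant or may require intervention to prevent one of the other outcomes" in the list.

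Section 5.2 opens the reporting window at consent: "Any events that are reported by the participant to have taken place from the time of signing the informed consent to study termination". It asks for all AEs to be reported, and for non-serious ones to be recorded. For SAEs it asks for a form to the Principal Investigator within 24 hours and for that person's opinion on whether the event was related and unexpected, which decides onward reporting. It then adds the exemption: "Note that hospitalisations for elective treatment of a pre-existing condition do not need reporting as SAEs".

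Section 2 lists safety as an objective: "ii) Safety: self-reported safety profile". Section 6.1.1 gives the record of prior disease: "Existing co-morbidities and medications will be collected via self-reporting".

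**The concern.** Exempting elective admissions is sensible when the admission reflects disease that was there at entry and has not changed. Such admissions are background and say nothing about the intervention. The note goes further, because it exempts every elective admission for a pre-existing condition, including one that became necessary because the condition worsened during the study.

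That matters here because participants are 60 or older, may use a walking aid, and report their co-morbidities, while the tool raises exercise volume and load in steps (section 3.1.1). Aggravation of an existing condition is therefore a foreseeable form of harm. The hypothesis in section 1.2 says the tool will be safe. At stake is whether such an event is classed as serious and receives the expedited form and the relatedness judgement that go with that class.

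**Working it through.** The protocol states no figure on this point, so the check sets the rules side by side.

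1. **Is the exemption qualified?** The note in 5.2 has two conditions: the treatment is elective and the condition is pre-existing. It does not ask whether the condition has worsened, whether the admission was planned before consent, or whether the event is unrelated to the exercises. It gives no reference date for pre-existing. No other section supplies these limits.

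2. **What would 5.1 say alone?** If existing disease worsens during the study in an untoward and unexpected way and has to be treated in hospital, the hospitalisation criterion is met and the event is an SAE.

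3. **What does 5.2 do to that event?** If the admission is elective, the note says it need not be reported as an SAE. The two sections then give different answers for the same event.

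4. **Does another clause in 5.1 close the gap?** The important-event sentence is written for events without hospitalisation, so it does not clearly reach an elective admission. The medical-judgement sentence could reach the underlying worsening, but the note is the more specific rule and concerns reporting. The text does not say which prevails.

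5. **What is lost?** Section 5.2 describes the 24-hour form and the Principal Investigator's judgement of relatedness and expectedness only for SAEs. Non-serious AEs are recorded, with no such judgement described.

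6. **What is not lost?** Unplanned admissions, deaths, life-threatening events and disabling events remain SAEs. The worsening itself is still reportable as an AE.

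**Size.** The number of events affected would be (participants) × (proportion with an elective admission for a pre-existing condition) × (share of those that followed in-study worsening). The documents give neither proportion, so the product cannot be computed.

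What can be shown is how sensitive a small count is, purely as illustration. Assume 500 in an arm, which section 4.1.1 gives as the maximum, and no other SAE. The exact (Clopper-Pearson) 95% upper limit for 0/500 is 1 − 0.025^(1/500) = 0.74%. For x > 0 it is the 97.5th centile of Beta(x + 1, 500 − x):

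| True SAEs | Upper limit if counted | Upper limit if all missed | Relative fall |
|---|---|---|---|
| 1 | 1.11% | 0.74% | (1.11 − 0.74)/1.11 = 33% |
| 2 | 1.44% | 0.74% | (1.44 − 0.74)/1.44 = 49% |
| 3 | 1.74% | 0.74% | (1.74 − 0.74)/1.74 = 57% |

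These rows say nothing about how likely one, two or three missed events are.

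**The case against.** The strongest reply is that little is actually lost. All AEs must be reported, participants have a form for logging events (section 5), and the follow-up questionnaires carry added safety items (section 4.1.4). The objective is a self-reported safety profile and not a count of SAEs. Medical judgement on seriousness applies in every situation, the worsening is an AE in its own right before any admission is booked, and the note permits non-reporting without forbidding reporting. Eligibility also narrows the risk: people with chest pain or dizziness on exercise are excluded, and participants must have no professional contraindication to gentle exercise.

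Most of this stands, and it confines the point to classification and expedited review. It does not remove the point. A permissive waiver leaves like cases open to different handling, and nothing says that medical judgement overrides the note.

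A reader might infer more: that aggravation of existing disease disappears from the serious-event profile, or that the comparison of serious events between arms is biased towards safety. The documents support neither. Only aggravations whose sole route to seriousness is an elective admission are exposed. No between-arm comparison of SAEs is planned in sections 2 or 4.1.5, the exemption applies equally to both arms, and controls also receive guidance promoting physical activity. That missed events would fall mainly in the tool arm is therefore an assumption.

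**Conclusion.** The point holds in a limited form. The note in 5.2 is unqualified and conflicts with the hospitalisation criterion in 5.1 for one class of event: disease present at entry that worsens after consent and becomes serious only through an elective admission. Such an event could be filed as a non-serious AE without the 24-hour form or the only relatedness review the protocol describes.

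This rests on a literal reading of the note and on the important-event sentence not reaching events with hospitalisation. The number of events affected is unknown, and the worsening itself stays in the AE data. It is a modest wording gap, worth closing because safety is a stated objective and the change is cheap.

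**What to change.** Reconcile 5.1 and 5.2 by adding a proviso to the note: the exemption for elective treatment of a pre-existing condition applies only if that condition has not worsened since consent; where it has worsened, the event is assessed against the SAE definition in 5.1.

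The proviso should not turn every other admission into an SAE. Section 5.1 still requires the event to be untoward and unexpected, and an admission booked after consent for an unchanged condition need not meet that test.

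Optionally, add a baseline question on admissions already planned or wait-listed, next to the co-morbidity items, so that use of the exemption can be checked. The proviso works without it.

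The cost is one sentence, a few more SAE forms and a slightly higher reported SAE count. Sample size and analysis do not change.
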